10. DATA HANDLING AND RECORD KEEPING

a. Registration Procedures

Subjects will be registered in C3PR, a cancer Biomedical Informatics Grid (caBIG® NCI) application.

b. Methods for Data Collection and Data Collection Tools

Data will be entered into OpenClinica through electronic web-based case report forms (CRFs) which replicate the paper CRFs attached to this protocol. OpenClinica is a secure open source system for electronic data capture and clinical data management. Data will be stored as required per regulations.

c. Confidentiality, Storage and De-Identification of Data

Government agency regulations and directives require that the study investigator retain all study documentation pertaining to the conduct of a clinical trial. Study documents should be kept on file until three years after the completion and final study report of this investigational study.

11. CRITERIA FOR EVALUATION**a. Outcome measures for Specific Aim 1**

i. Primary efficacy outcome:

- Excessive Toxicity, which will be defined as an acute radiation-toxicity score of 2 or higher on either Day 12 (the last day of APBI) or at the one-month follow-up visit. Acute radiation toxicity will be scored as described below using the RTOG Acute toxicity-scoring criteria.

ii. Secondary efficacy outcomes:

- Acute radiation toxicity, which will be scored using the RTOG Acute toxicity-scoring criteria. These range from 0 (no change) to 4 (necrosis). Acute radiation toxicities will be scored on Day 0 (baseline, a week before APBI), Day 12 (the last day of APBI), and at the one-month follow-up visit.

- A score of 2 or higher on the RTOG Acute scale will be considered to be excessive toxicity if it is scored on either Day 12 or at the one-month follow-up visit (see Excessive Toxicity above).

- Chronic radiation toxicity, which will be scored using RTOG LENT/SOMA criteria. These range from Grade 1 (minimal hypersensation) to Grade 4 (refractory). Chronic radiation toxicities will not be scored at baseline, but will be scored during the follow-up visits at 6, and 12 months.

- Breast cosmesis, which will be scored using a subject-and-physician point-scoring system. Breast cosmesis will be scored at Day 0 (baseline), Day 12 (the last day of APBI), and during the 1 month, 6 month, and 12 month follow-up visit.

- Breast density, which will be determined by mammogram at baseline and during the follow-up visits at 6 and 12 months.

- Performance Status, which will be assessed using questionnaire. Performance status will be assessed on Study Days 0, 12, and during the follow-up visits at 1 and 6 months.

- Quality of life, which will be determined using questionnaire. The quality-of-life questionnaire will be assessed on Study Days 0, 12, and during the follow-up visits at 1 and 6 months.

- An open-ended question (How was your experience with this treatment?), which will be answered by the subject. An open-ended question will be assessed during the follow-up visits at 1 and 6 months.

- Additional subject data to be collected will be BMI, meds, steroids, smoking, alcohol, etc. Stratification using these criteria will be considered but unlikely to be significant in this small pilot trial.

b. Outcome measures for Specific Aim 2

Assays of all outcome measures will be performed on blood samples obtained at the following times from each subject: Day 0 (baseline, the day before GLN/placebo begins), Day 8 (just before APBI commences), Day 10 (the third day of APBI), Day 12 (the last day of APBI), and at the 1-month follow-up visit (the day when GLN/placebo ends).

- Measures of oxidative stress, antioxidant defense and a potential biomarker for GLN effect:
 - Levels of enzymatic antioxidants such as glutathione peroxidase (GPx), glutathione S-transferase (GST), superoxide dismutase (SOD), and catalase (CAT).
 - Levels of non-enzymatic antioxidants, namely, glutathione in both its reduced (GSH) and oxidized (GSSG) form.
 - Reactive oxygen species such as the superoxide anion (O_2^-) and hydrogen peroxide (H_2O_2).
 - Lipid peroxidation products such as malondialdehyde (MDA) and/or 4-hydroxynonenal (4-HNE).
 - DNA-oxidation products such as 8-hydroxy-2'-deoxyguanosine (8-OHdG).
 - Protein-oxidation markers such as the carbonyl derivatives of proline, lysine, arginine and threonine residues.
 - A potential biomarker for GLN effect such as myoglobin.
- Measures of immune response:
 - Complete blood count (CBC)
 - NK-cell activity.
 - Production of cytokines such as interferon-gamma (IFN- γ) and tumor necrosis factor-alpha (TNF- α).

12. STATISTICAL CONSIDERATIONS

a. Sample Size and Power

Sample-size considerations are motivated by the statistical analysis plan for the primary efficacy outcome (see below), in which a two-sided Fisher's exact test will be used at 10% alpha to compare the glutamine arm to the placebo arm for a statistically significant decrease in the proportion of excessive toxicities. Rubio *et al.*¹⁷ reported the results of a pilot study of oral glutamine supplementation versus placebo in 17 breast-cancer subjects receiving radiation as part of breast-conservation therapy. By the 7th week of their study, all 8 subjects taking placebo (100%), but only 4 of 9 subjects taking glutamine (44%), experienced scores of ≥ 2 on the RTOG Acute toxicity scale. Their results are consistent with excessive-toxicity rates of at least 90% on the placebo arm, but at most only 50% on the glutamine arm. To calculate power, we hypothesize that excessive toxicity rates in our study will be equal to 50% with glutamine versus 90% with placebo. Calculations using PASS 12 software¹⁸ show that a total of 50 study subjects, 25 randomized to the glutamine arm and 25 randomized to the placebo arm, give the two-sided Fisher's exact test 91.1% power at 10% alpha to detect the hypothesized difference in excessive-toxicity rates between the glutamine arm and the placebo arm. This result demonstrates that 25 subjects per study arm (50 subjects total) give this proposed study sufficient

power to achieve the radiation-toxicity-reduction part of its primary objective. To protect against dropouts, a total of 60 subjects will be enrolled and randomized in order to ensure that 50 subjects complete the study.

b. Statistical analysis plan for Specific Aim 1

i. Analysis plan for the primary efficacy outcome

The number of excessive toxicities on each study arm will be reported both as a raw count and as a proportion of the number enrolled per arm. The study-arm difference in excessive-toxicity proportions will be tested for statistical significance using a two-sided Fisher's exact test at an alpha=10% significance level.

ii. Analysis plan for the secondary efficacy outcomes

Data for each secondary-efficacy outcome measure will be summarized by assessment time and study arm, using mean scores and proportions for Likert-scaled data (acute radiation toxicity, chronic radiation toxicity, and performance status), and using means and standard deviations (SDs) for continuous and quasi-continuous data (breast cosmesis, and quality of life). Data will be graphed versus assessment time as stacked barcharts or profile plots depending on the outcome measure. Treatment-arm differences over time will be assessed using longitudinal-analysis methods, namely, (A) logistic and cumulative-logistic regressions with generalized estimating equations for dichotomized and Likert-scaled data, respectively, and (B) repeated-measures ANOVAs for continuous and quasi-continuous data. Post-hoc comparisons between study arms at each time point will employ an alpha=5% significance level despite the multiple testing, in order not to inflate Type II error in this pilot Phase II study.

c. Statistical analysis plan for Specific Aim 2

For each assay endpoint, data will be summarized by study arm and collection timepoint as means and SDs, and graphed versus time as profile plots. Adherence to distributional assumptions will be examined, and data transformations will be applied if warranted. Repeated-measures ANOVA will be used to compare each assay endpoint for study-arm differences over time. Post-hoc comparisons between study arms at each time point will employ an alpha=5% significance level despite the multiple testing, in order not to inflate Type II error in this pilot Phase II study.

d. Missing, Unused and Spurious Data

Missing data will be treated as missing, and will not be imputed. Spurious data will be corrected at the source document. Any data documented as spurious that is unable to be corrected at the source will be treated as missing.

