4. TRIAL OBJECTIVES AND AIMS

a. Primary Objective

To determine if oral GLN will reduce radiation toxicity for subjects undergoing BCT.

b. Aim 1

Evaluate GLN as an agent to prevent acute and late radiation toxicities and improve the quality of life for subjects undergoing BCT.

We will investigate oral GLN treatment in a cohort of 50 subjects diagnosed with DCIS, or Stage I or II invasive breast cancer, undergoing accelerated partial breast irradiation (APBI) as part of BCT. Subjects will be randomized in a 1:1 ratio to receive GLN versus placebo and followed daily during the treatment with APBI and then at 1, 6 and 12 months after APBI to determine differences in clinically evident acute and late radiation toxicity through multiple assessments. The primary efficacy outcome will be excessive toxicity, which will be defined as a score of 2 or higher using the RTOG Acute scale of radiation-toxicity criteria when scored on either the 12-day or 30-day assessment time.

c. Aim 2

Elucidate the mechanisms of GLN effects by examining the antioxidant defense and immune response in host.

To examine antioxidant defense, we will measure non-enzymatic and enzymatic antioxidants, reactive oxygen metabolites, lipid peroxidation, oxidative DNA damage, and protein oxidation in subjects treated with GLN versus placebo. We will also test a potential biomarker for the GLN effect. To evaluate the immune response, we will measure complete blood count, NK cell activity, and cytokine production in these subjects.

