- Blood will be drawn for the measurements of non-enzymatic and enzymatic antioxidants, reactive oxygen metabolites, lipid peroxidation, oxidative DNA damage, protein oxidation, myoglobin, complete blood count, NK cell activity, and cytokine production. Blood (approximately 45ml) will be collected in Sodium Heparin (green top) tubes and 5 ml blood collected in serum (red top) tubes.
- A quality of life questionnaire will be completed by the subject.
- Performance status will also be determined.
- The subject will have breast skin graded by RTOG acute scoring system.
- A subject and physician point scoring system for breast cosmesis will be completed.
- The next appointment for the subject will be made and subject will be released from the UAMS Radiation Oncology Center.
- Adverse Event assessment

Month 1 Visit:

- The subject will complete GLN/placebo.
- Subject will return any unused GLN/placebo to monitor treatment compliance (measure unconsumed product). This will be used to measure compliance as a percentage of product dose taken. It will also be used to correlate with serum levels of glutamine. Analysis will be performed on intent to treat.
- Glutamine diary will be returned to the study personnel.
- Blood will be drawn for the measurements of non-enzymatic and enzymatic antioxidants, reactive oxygen metabolites, lipid peroxidation, oxidative DNA damage, protein oxidation, complete blood count, NK cell activity, and cytokine production. Blood (approximately 45ml) will be collected in Sodium Heparin (green top) tubes and 5 ml blood collected in serum (red top) tubes.
- A quality of life questionnaire will be completed by the subject.
- Performance status will also be determined.
- The subject will have breast skin graded by RTOG acute scoring system.
- A subject and physician point scoring system for breast cosmesis will be completed.
- An open-ended question for subjects regarding their experience with the study supplement (glutamine/placebo) and radiation treatment will be completed by the subjects.
- Subjects will be examined for recurrence.
- Adverse Event assessment
- The next appointment for the subject will be made and subject will be released from the either the UAMS Breast Surgical Oncology clinic or the UAMS Radiation Oncology Center.

Month 6 Visit:

- A bilateral mammogram will be performed.
- The subject will continue to be grade by per guidelines on RTOG LENT/SOMA Scoring System.

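### Section 12.b.i puts the primary proportion over all enrolled subjects and gives no rule for those without an RTOG Acute score, so read literally they count as free of excessive toxicity

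*Combined protocol and SAP*

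**What the plan says.** Section 12.b.i gives one denominator for the primary outcome. Excessive toxicities "will be reported both as a raw count and as a proportion of the number enrolled per arm". The next sentence reads "The study-arm difference in excessive-toxicity proportions will be tested for statistical significance", by a two-sided Fisher's exact test at 10% alpha, and names no denominator of its own.

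Four other places bear on the point:
- Sections 4.b and 11.a define the event as an RTOG Acute score of 2 or higher on Day 12 or at one month. Neither says how to classify a subject with no score, or with one score that is below 2.
- Section 12.d: "Missing data will be treated as missing, and will not be imputed".
- Section 12.a bases its 91.1% power on 50 subjects, "25 randomized to the glutamine arm and 25 randomized to the placebo arm", and then states that "a total of 60 subjects will be enrolled and randomized in order to ensure that 50 subjects complete the study".
- Section 7.d, in the Month 1 item on product compliance: "Analysis will be performed on intent to treat". This indicates who is analysed, not what value an unscored subject takes.

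**The concern.** If observed events are divided by everyone enrolled, a subject with neither score stays in the denominator and cannot enter the numerator. In effect she is imputed as having no excessive toxicity, although 12.d rules out imputation. The plan expects 90% of placebo subjects to have the event, so most unscored placebo subjects would be misclassified, and the expected difference between arms shrinks. The power calculation, in contrast, treats 25 per arm as the number analysed after losses.

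Such subjects can arise. Randomisation takes place at the baseline visit (7.d), up to 2 weeks may pass before Day 1 (Section 8, footnote e), and irradiation starts only on Day 8. A subject who leaves in that interval may have no post-baseline score.

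At stake is the trial's one primary test. The same data can give different verdicts under two denominators, and the plan does not settle which the test uses.

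**Working it through.** **Inputs.** From 12.a and 12.b.i: event rates of 50% (glutamine) and 90% (placebo), two-sided Fisher's exact test, alpha 0.10, 60 randomised. From 4.b: 1:1 allocation. Assumed: exactly 30 per arm. The number of unscored subjects (m_G on glutamine, m_P on placebo) is not in the documents, so a range is shown. The plan's allowance of 60 − 50 = 10 is taken as a ceiling.

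**Formula.** Power = Σ_x Σ_y Bin(x; n_G, p_G) · Bin(y; n_P, p_P) · 1[Fisher p ≤ 0.10], with n_G = 30 − m_G and n_P = 30 − m_P. The enrolled denominator tests x/30 against y/30. The scored denominator tests x/n_G against y/n_P.

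**Plan's own figure.** With 25 per arm and none missing, the sum is 91.14%, matching the stated 91.1%. With 30 per arm all scored it is 95.4%.

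**The mechanism at 5/5 unscored.** Expected proportions over those enrolled are 0.50 × 25/30 = 41.7% and 0.90 × 25/30 = 75.0%. The difference falls from 40 to 33.3 points. Power is 81.3% on the enrolled denominator and 91.1% on the scored one.

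**Unscored subjects split between arms by chance.** The number on glutamine is hypergeometric (60, 30, M) and power is averaged over the split.

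| Unscored of 60 | Power, enrolled | Power, scored |
|---|---|---|
| 2 | 92.9% | 95.4% |
| 3 | 91.3% | 95.6% |
| 4 | 89.5% | 94.8% |
| 6 | 85.4% | 94.3% |
| 10 (ceiling) | 76.5% | 92.4% |

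The two denominators give different verdicts in 3.3% of trials at 2 unscored, 6.3% at 4, 10.0% at 6 and 17.2% at 10. The scored column is not quite monotone because unequal arm sizes make Fisher's test less discrete.

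**Fixed splits (glutamine/placebo), power enrolled vs scored.** 1/1: 93.9% vs 94.6%. 2/2: 91.7% vs 93.8%. Unequal loss works in both directions: 1/3 gives 81.8% vs 95.5%, and 3/1 gives 96.9% vs 95.6%.

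**False positives, 90% in both arms, enrolled vs scored.** 1/1: 1.4% vs 2.5%. 3/1: 3.7% vs 5.2%. 3/0: 10.55% vs 6.1%. 4/0: 18.0% vs 5.8%. At 3/0 with 80% or 70% in both arms, the enrolled figure is 9.4% or 8.4%. With a chance split at 90% in both arms it is at most 5.2% for the totals computed, up to 10 of 60.

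**Illustration only.** Take 18 glutamine and 24 placebo events with 1/3 unscored. Then 18/30 vs 24/30 gives p = 0.158, and 18/29 vs 24/27 gives p = 0.030. This is an adverse split; with 4 unscored, exactly 1/3 arises by chance about 25% of the time.

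**The case against.** The best defence is that the sentence naming the denominator governs reporting. The test sentence names none, and a statistician could apply 12.d to the test and drop unscored subjects. That stands in part: the link from report to test is a literal reading, not an explicit statement. But the plan offers no other denominator, and the defence itself requires a choice that the plan does not make.

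A second defence is that an enrolled denominator fits intent to treat. It does, and the denominator is not wrong in itself. What is missing is a stated value for subjects without a score.

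Three stronger readings are tempting and are not supported:
- A reader might take the 11.a wording, that a score "will be considered to be excessive toxicity if it is scored on either Day 12 or at the one-month follow-up visit", to mean that unscored subjects are non-events by definition. That item is listed under the secondary outcomes and fixes the timing of the event, as does 4.b with "when scored on either the 12-day or 30-day assessment time". The point rests on the denominator alone.
- A reader might infer that enrolling 60 protects power only if unscored subjects leave the denominator. The figures contradict this: enrolled-denominator power stays at or above 91.1% up to 3 of 60 by chance, and at 2/2.
- A reader might infer that true power is about 81%, or that false positives are generally inflated. The first needs all 10 allowed losses to lack both scores, 5 per arm. Completing the study may mean reaching Month 12, and a subject lost after Month 1 already has the primary outcome. The second needs one-sided loss from glutamine, which blinding makes less likely.

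**Conclusion.** The point holds as a defect of low to moderate severity. The only denominator in 12.b.i turns an unscored subject into a non-event when followed literally. That conflicts in spirit with 12.d and does not match the basis of the power figure in 12.a.

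Under the plan's own rates and 30 per arm, the cost is small for 1 to 3 unscored subjects. By chance split, power first drops below the stated figure at about 4 of 60, and it reaches 76.5% only at the ceiling of 10. Error above the nominal 10% needs about 3 or more losses, all on glutamine, with a rate near 90% in both arms. The number of subjects who will lack both scores is not given and is probably low, because both visits must be missed. The case for acting is that this is the single primary test, the rule is undecided, and settling it is cheap before the treatment codes are broken.

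**What to change.** In 12.b.i, use one denominator for both the report and the Fisher test: randomised subjects, analysed as randomised, with at least one post-baseline RTOG Acute score (Day 12 or Month 1). Then:
- classify once-scored subjects by the available score, in the same way in both arms;
- report unscored and once-scored subjects by arm;
- add one sensitivity analysis on all randomised subjects that counts unscored subjects, and those whose single score is below 2, as events in both arms;
- cross-refer 12.d and the intent-to-treat sentence in 7.d to this rule.

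Applied to unscored subjects split by chance, the sensitivity analysis keeps power of 94.5%, 93.3% and 88.7% at 2, 4 and 10 of 60, with false positives of at most about 2.5% at 90% in both arms.

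The cost is a few sentences and one short table. There are three downsides. The primary set may be smaller than all randomised, which departs from a strict intent-to-treat reading. Its result is unbiased only if missingness is unrelated to toxicity. The available-score rule keeps a favourable default for once-scored subjects, since it can miss events first seen at Month 1. For example, take 90% in both arms and 4/0 subjects scored on Day 12 only. False positives are then 6.9% if half of events first appear at Month 1 and 11.5% if three quarters do (assumed shares); with 2/2 they are 2.5% and 1.8%. The sensitivity analysis is therefore a required part of the change.

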Block randomization will be done using randomly chosen block sizes of 2, 4, and 6 to maximize the likelihood that treatment arms will have equal numbers of patients. Randomization will be done by sealed envelopes located at the UAMS Research Pharmacy. There will be one set of consecutively numbered envelopes. At each randomization, the lowest numbered envelope in the set will be chosen. The Pharmacist will open the envelope and assign the subject to the treatment arm based on the contents of the envelope.

Based on the results of the randomization, the appropriate treatment will be dispensed to the subject. A list of randomized subjects will be kept confidential and securely stored in the UAMS Research Pharmacy.

- Methods for ensuring blinding

Only the UAMS Research Pharmacy staff will be unblinded. The blinded drugs and the blinded code will be stored in a safe and secure location in the UAMS Research Pharmacy.

- Methods for unblinding the study

Upon completion of the study: The drug codes will be broken and made available to the Statistician, the Principal Investigator and the Co-investigator for final data analysis.

PROCEDURE FOR UNBLINDING IN CASE OF MEDICAL EMERGENCY: In the event of medical emergency, the treating physician will contact the UAMS Research Pharmacy to unblind the patient's treatment assignment. A subject's treatment assignment should only be unblinded when knowledge of the treatment is essential for further management of the subject. Unblinding for any other reason will be considered a protocol deviation. Unblinding must be documented in the subject's CRF.

Arms	Assigned interventions
Placebo – Group 1	Powdered Dextrose, 8.33 grams by mouth TID for 30 days, so that daily dose is 25 grams per day.
Glutamine – Group 2	Powdered Glutamine, 10.0 grams by mouth TID for 30 days, so that daily dose is 30 grams per day. .

c. Specimen Handling

Blood (approximately 45ml) will be collected in Sodium Heparin (green top) tubes and 5 ml blood collected in serum (red top) tubes. Samples will be collected in the Cancer Institute Blood Draw station or the Infusion room by a trained personal. Tubes will be labeled with each subject's unique identification number or code. Tubes will be delivered to [name] laboratory for analysis.

d. Visit Breakdown

Baseline Visit:

- The subject will sign the consent form.
- A quality of life questionnaire will be completed by the subject.
- Performance status will also be determined.

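### Optional improvement: Boschloo's exact test would use more of the plan's 10% alpha than Fisher's and raise power from 91.1% to 94.2% at 25 per arm, usually by less with unequal arms

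*Combined protocol and SAP*

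**What the plan says.** Section 12.b.i specifies one test for the single primary outcome: the arm difference "will be tested for statistical significance using a two-sided Fisher's exact test at an alpha=10% significance level". Section 12.a sizes the trial on the same test. There, "we hypothesize that excessive toxicity rates in our study will be equal to 50% with glutamine versus 90% with placebo". With 25 per arm, these assumptions are said to "give the two-sided Fisher's exact test 91.1% power at 10% alpha".

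Three further statements bear on how much the choice of test matters:

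- Section 12.a describes the pilot results as "consistent with excessive-toxicity rates of at least 90% on the placebo arm, but at most only 50% on the glutamine arm", so the design rates are treated as bounds.
- Section 12.a also says that "a total of 60 subjects will be enrolled and randomized in order to ensure that 50 subjects complete the study", so the analysed arms could hold anything from about 25 to 30 subjects each.
- Section 7.b states that "Block randomization will be done using randomly chosen block sizes of 2, 4, and 6", which keeps the arms close in size but does not make them equal after dropout.

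The plan does not give the attained size of Fisher's test and names no other exact test.

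**The concern.** Fisher's test conditions on the total number of events. With small, equal arms few p-values are attainable, so a nominal 10% test can have a true error rate well below 10%. The sponsor chose a 10% two-sided error rate, and part of that allowance goes unused.

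An unconditional exact test built on the same p-value can recover some of it without breaching 10%. At stake is a modest amount of power for the only primary test in a trial sized for 50 completers. Neither the validity of the trial nor the correctness of its power statement is in question.

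**Working it through.** **Inputs.** From 12.a and 12.b.i: two-sided Fisher, alpha 0.10, 25 per arm, placebo rate 0.90, glutamine rate 0.50, stated power 91.1%. Also from 12.a: pilot rates 8/8 = 100% on placebo and 4/9 = 44% on glutamine. Assumed here: final arms of 23 to 30 with an imbalance of at most 4, which gives 52 ordered placebo/glutamine pairs (8 equal, 44 unequal).

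**Method.** Enumerate every table (x, y), with x ~ Bin(n₁, p₁) on placebo and y ~ Bin(n₂, p₂) on glutamine; at 25/25 there are 26 × 26 = 676.

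- Fisher two-sided p (minimum-likelihood version) = sum of the hypergeometric probabilities no larger than that of the observed table. Reject if p ≤ 0.10.
- Power = Σ Bin(x; n₁, 0.90) · Bin(y; n₂, 0.50) over rejected tables.
- Size = maximum over a common rate p of Σ Bin(x; n₁, p) · Bin(y; n₂, p) over rejected tables.
- Boschloo: reject if the Fisher p ≤ c, where c is the largest cutoff with size ≤ 0.10.

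**Step 1: the plan's own figure.** At 25/25 Fisher rejects 404 of 676 tables, and its power is 0.9114. The stated 91.1% is correct.

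**Step 2: Fisher against Boschloo at 25/25.** The Boschloo cutoff is c = 0.1482. The next attainable value, 0.1536, would have size 10.2%. Boschloo rejects 428 tables: Fisher's 404 plus 24 with Fisher p from 0.110 to 0.148.

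| 25/25, nominal 10% | Fisher | Boschloo |
|---|---|---|
| Maximum size | 6.49% | 9.44% |
| Size at common rate 70% | 5.4% | 9.0% |
| Size at common rate 90% | 2.9% | 5.3% |
| Power, 90% vs 50% | 91.1% | 94.2% |

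The gain is 94.2 − 91.1 = 3.1 points. Boschloo does not use all of the alpha either, as the row for a common rate of 90% shows. In terms of patients, Fisher has 93.8% power at 28 per arm and 94.6% at 29, so it needs 29 per arm to match Boschloo at 25: 58 − 50 = 8 more subjects.

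**Step 3: other arm sizes, 90% vs 50%.**

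| Placebo/glutamine | Fisher max size | Fisher power | Boschloo power | Gain (points) |
|---|---|---|---|---|
| 24/25 | 8.6% | 91.9% | 93.2% | 1.3 |
| 25/24 | 8.6% | 93.5% | 94.6% | 1.1 |
| 26/24 | 8.4% | 92.8% | 95.0% | 2.2 |
| 23/27 | 8.9% | 91.3% | 94.7% | 3.3 |
| 27/23 | 8.9% | 93.3% | 94.4% | 1.1 |
| 30/30 | 5.6% | 95.4% | 97.5% | 2.1 |

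Gains are computed before rounding. Over the 52 pairs, the 8 equal ones gain 2.1 to 3.6 points. The 44 unequal ones gain 0.04 to 3.3, median 1.1 (20 below 1 point, 15 from 1 to 2, 9 above 2). Fisher's maximum size at the unequal pairs is 7.2% to 9.2%. Boschloo power runs from 91.8% (23/23) to 97.5% (30/30). Boschloo rejected every table that Fisher rejected in all 52 pairs.

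**Step 4: other true rates at 25/25.**

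| Placebo vs glutamine | Fisher | Boschloo |
|---|---|---|
| 100% vs 44% (both pilot rates) | 99.99% | 100.0% |
| 90% vs 44% (pilot glutamine rate) | 96.1% | 97.8% |
| 90% vs 60% (assumed) | 73.3% | 79.0% |
| 85% vs 55% (assumed) | 67.1% | 75.1% |
| 80% vs 50% (assumed) | 63.8% | 72.6% |

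The gain all but vanishes if the contrast is as large as in the pilot. It reaches 6 to 9 points for the assumed smaller contrasts.

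**Step 5: which two-sided Boschloo.** A common alternative doubles the smaller one-sided p-value. It gives the same result at 25/25 and 30/30, but not at unequal arms: 94.3% against 93.2% power at 24/25, and 93.9% against 94.7% at 23/27. At each of these two splits the doubled version also fails to reject 2 tables that minimum-likelihood Fisher rejects.

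**The case against.** Fisher's test is valid, is used consistently in 12.a and 12.b.i, and has its power stated correctly. On that view, choosing Boschloo is a preference between two sound tests.

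The 25/25 comparison is also among the most favourable to Boschloo. Only three of the 52 pairs (23/23, 24/24 and 23/27) show a larger gain. Once the arms differ by a single subject, Fisher's maximum size can already reach 9.2%, against 9.2% for Boschloo at 25/26. Section 12.b.i reports proportions of the number enrolled, and the Month 1 visit text in 7.d calls for an intention-to-treat analysis, so the analysed number may be nearer 60. At 30/30 Fisher already has 95.4% power, and at 29/30 or 30/29 the gain is only 0.5 to 0.6 points. Finally, Boschloo is less familiar, its two-sided versions differ, and some significant results would carry a Fisher p-value above 0.10.

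Most of this stands, and it is why the point is optional. It does not remove the point. The plan's own power basis is 25 per arm, the specified Boschloo version loses no rejection that Fisher would make, and type I error stays within the sponsor's chosen limit. Section 12.d leaves missing data unimputed, so 25/25 remains a reasonable planning case.

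**Conclusion.** The point holds as a low-priority improvement, not an error. At 25/25 and 90% versus 50%, Boschloo's test raises power from 91.1% to 94.2%, with maximum size 9.44% instead of 6.49%.

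A typical gain is 2 to 4 points with equal arms and about 1 point with unequal arms, with exceptions such as 3.3 points at 23/27. These figures rest on independent binomial outcomes, the minimum-likelihood two-sided Fisher p-value, the plan's design rates, and the assumed range of final arm sizes.

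**What to change.** Before unblinding, replace the test sentence in 12.b.i with wording such as:

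> Excessive-toxicity proportions in the two arms will be compared by Boschloo's two-sided unconditional exact test at alpha = 10%, ordering tables by the two-sided (minimum-likelihood) Fisher p-value and maximising the p-value over the common rate.

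Confirm that the chosen software runs this version at unequal arm sizes. In 12.a, restate power as about 94% for 25 per arm at 90% versus 50%, varying from about 92% to 98% for final arms of 23 to 30. Label any Fisher p-value as descriptive.

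The cost is SAP text and a software check, with no extra patients or data. The team should accept in advance that the two tests can disagree. For 21/25 versus 15/25, for example, Fisher gives p = 0.114 and Boschloo p = 0.065. If the sponsor prefers to keep Fisher's test for familiarity, the plan remains sound as written.
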